#### 4.13 Iron supplement dosage

The dose of iron supplements is defined by the following formula. However, the dose of iron supplements will not be calculated if iron supplements are used as needed.

Mean monthly dose of iron supplements during the screening period\* and each scheduled study visit period\* (tabulation period of iron supplements) = (Daily dose based on the physician’s prescription  $\times$  Period of administration (days) of the corresponding dose during the tabulation period of iron supplements)/Tabulation period of iron supplements (days)  $\times$  30.4375

\*: The number of days of the screening period is “First day of the treatment period – First day of the screening period.”

\*2: For each period between the scheduled study visits, the actual study visit dates are not considered, and this tabulation is fixed as follows:

- ✓ The first day of the treatment period to Week 2 of the treatment period: The first day of the treatment period (Day 1) to Day 14
- ✓ Week 2 of the treatment period to Week 4 of the treatment period: Days 15 to 28
- ✓ The same should apply thereafter, and the final period between the scheduled study visits should be Week 48 to Week 52 of the treatment period: Day 337 to the day before the day of blood sampling for hematology tests at Week 52 of the treatment period. However, for subjects who discontinued their treatment, the final period between the scheduled study visits should be up to the day before discontinuation.

\*3: If there are multiple applicable doses, the sum of the calculated values for each dose should be used.

\*4: For subjects who discontinued their treatment, the final period between the scheduled study visits (days) should be the actual number of days until the day before discontinuation.

\*5: In this tabulation, 1 month is counted as 30.4375 days (365.25/12 = 30.4375).

## 4.14 Kt/V

Kt/V is defined by the following equation. It should be calculated based on the first day of treatment period, Week 24, Week 52, and the day of discontinuation. All items used for the calculation of Kt/V should be those measured on the same day.

$$Kt/V = -\ln(Ct/C0 - 0.008 \times t) + (4 - 3.5 \times Ct/C0) \times (BW0 - BWt)/(BWt)$$

t: Dialysis time, C0: BUN concentration before dialysis, Ct: BUN concentration after dialysis, BW0: Body weight before dialysis, BWt: Body weight after dialysis

## 4.15 QOL (EQ-5D-5L) index value

Responses to 5 questions (mobility [Mo], self care [Sc], usual activities [Ua], pain/discomfort [Pd], anxiety/depression [Ad]) in 5 levels (level 1 is healthy and the level goes up to 5, and the health status decreases with increases in level) are converted into index values. The index value is calculated using the Japanese EQ-5D-5L conversion table (Table 4.15.1).[1]

- (1) The responses to questions from Mo to Ad should be arranged side by side into five numbers (hereinafter, health state). The health state can exist from “11111” to “55555.”
- (2) If all five responses are 1, i.e. the health state is “11111”, the index value is 1. If the health state is other than “11111,” “Constant term: -0.060924” in Table 4.15.1 and the estimated value of the coefficient for each level of the response to each question should be used to obtain the index value using the following formula. The index value of the subject should be missing if one of the 5 questions has not been answered.

Index value = 1 + “Estimate of the constant term” + “Sum of ‘estimated coefficients corresponding to levels of responses other than 1’”

Table 4.15.1 Japanese EQ-5D-5L conversion table

Item	Level	Estimate	Standard error	p value
Constant term		-0.060924	0.013625	<0.0001
Mo	2	-0.063865	0.008996	<0.0001
	3	-0.112618	0.009287	<0.0001
	4	-0.179043	0.010231	<0.0001
	5	-0.242916	0.009425	<0.0001
Sc	2	-0.043632	0.008931	<0.0001
	3	-0.076660	0.009972	<0.0001

	4	-0.124265	0.010129	<0.0001
	5	-0.159659	0.008924	<0.0001
Ua	2	-0.050407	0.009205	<0.0001
	3	-0.091131	0.010005	<0.0001
	4	-0.147929	0.009744	<0.0001
	5	-0.174786	0.009115	<0.0001
	2	-0.044545	0.008354	<0.0001
Pd	3	-0.068178	0.010052	<0.0001
	4	-0.131436	0.008985	<0.0001
	5	-0.191203	0.009604	<0.0001
	2	-0.071779	0.009701	<0.0001
Ad	3	-0.110496	0.010863	<0.0001
	4	-0.168171	0.009850	<0.0001
	5	-0.195961	0.009164	<0.0001

Mo: mobility, Sc: self care, Ua: usual activities, Pd: pain/discomfort, Ad: anxiety/depression

## 4.16 QOL (KDQOL) scoring

Step 1 (See Table 4.16.1): The appropriate score is converted from the response choices for each item number in Table 4.16.1 for each subject.

Table 4.16.1 Step 1 in KDQOL scoring

Item number	Response choices	Score
Question 4 A–D	1	0
Question 5 A–C, Question 21	2	100
Question 3 A–J	1	0
	2	50
	3	100
Question 19 A, B	1	0
	2	33.33
	3	66.66
	4	100
Question 10	1	0
Question 11 A, C	2	25
Question 12 A–D	3	50
	4	75
	5	100
Question 9 B, C, F, G, I	1	0
Question 18 B	2	20
	3	40
	4	60
	5	80
	6	100
Question 20	1	100

	2	0
Question 1, Question 2, Question 6, Question 8	1	100
Question 11 B, D, Question 14 A–M	2	75
Question 15 A–H, Question 16 A, B	3	50
Question 24 A, B	4	25
	5	0
Question 7	1	100
Question 9 A, D, E, H	2	80
Question 13 A–F	3	60
Question 18 A, C	4	40
	5	20
	6	0
Question 23	1	100
	2	83.33
	3	66.66
	4	50
	5	33.33
	6	16.66
	7	0

Step 2 (See Table 4.16.2): The mean of the scores calculated at Step 1 in the item numbers in the right column of Table 4.16.2 should be calculated for each subject by subscale. For questions 17 and 22, the scores obtained are multiplied by 10 to convert the values from 0 to 100. The mean value should be the score for each subject by subscale. If at least one question constituting the subscale is answered, the subscale should be tabulated without missing. If “No” is chosen in question 16, the question 16 should be treated as missing.

Table 4.16.2 Step 2 in KDQOL scoring

- Each item score should be averaged to calculate each subscale score

Subscale	Number of items	After scoring according to Table 4-1, the mean of the items included in each subscale should be calculated.
Kidney disease-specific scale		
Symptoms	12	Questions 14 A–K, L (M)*
Effects of kidney disease on daily life	8	Question 15 A–H
Burden due to kidney disease	4	Question 12 A–D
Working status	2	Question 20, Question 21
Cognitive function	3	Question 13 B, D, F
Relationship with people	3	Question 13 A, C, E
Sexual function	2	Question 16 A, B
Sleep	4	Question 17, Question 18 A–C
Social support	2	Question 19 A, B
Encouragement from dialysis staff	2	Question 24 A, B
Patient satisfaction with dialysis care	1	Question 23
Comprehensive scale (SF-36)		

Physical functioning	10	Question 3 A–J
Daily role functioning (physical)	4	Question 4 A–D
Bodily pain	2	Question 7, Question 8
General health	5	Question 1, Question 11 A–D
Vitality	4	Question 9 A, E, G, I
Social functioning	2	Question 6, Question 10
Daily role functioning (emotional)	3	Question 5 A–C
Mental health	5	Question 9 B, C, D, F, H

## 5. Analysis Sets

Efficacy analysis will be performed in the full analysis set (hereinafter, FAS). Safety analysis will be performed in the safety analysis set.

The analysis sets are defined below. Details of treatment of subjects regarding the final fixed data will be decided by the sponsor before fixing the data.

### 5.1 Efficacy analysis set

#### (1) FAS

The FAS consists of all randomly allocated subjects excluding the following subjects:

- ✓ Subjects who did not have anemia associated with HD-CKD
- ✓ Subjects who have never received a dose of the study drug
- ✓ Subjects with no post-randomization efficacy data

### 5.2 Safety analysis set

The analysis set consisting of all randomly allocated subjects excluding the following subjects:

- ✓ Subjects who have never received a dose of the study drug
- ✓ Subjects with no post-randomization safety data

## 6. Patient Cohort

The patient cohort is defined as follows:

Conversion cohort: A group of patients who have received ESA formulations from 8 weeks prior to the first day of the screening period.

## 7. Data Handling

Final fixed data should be handled as follows: The handling of data other than the following should be decided in the case review meeting and specified in the statistical analysis plan that will be fixed finally by the data fixation.

### 7.1 Handling of missing data

If test measurements are missing or if problems with samples etc. result in invalid measurements or reference values, these should be handled as missing values. Derived variables should also be treated as missing if even a single test value or other data required for derivation is missing or not adopted.

### 7.2 Handling of data for tabulation at each evaluation time point

Data that meet the permitted range specified in the “Table 9.1-1 Permitted ranges for study visits” section of the study protocol should be used for the tabulation at each evaluation time point and should not be imputed with those outside the permitted range.

If there are multiple data within the permitted range, then the one closer to the reference date should be adopted. If the deviations from the reference date are the same, data for the efficacy and safety evaluations should be adopted before and after the reference date, respectively.

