Iron supplements																												X		

Blood sampling for genetic analysis performed once as early as possible after Week 2 of treatment period
 Blood sampling for genetic analysis performed once as early as possible after Week 2 of treatment period
 Administered according to the dosage adjustment guidelines
 Administered according to the dosage adjustment guidelines
 Iron supplements administered to maintain a serum ferritin level of ≥ 100 ng/mL or a TSAT of $\geq 20\%$

- [a] Maximum screening period length is 6 weeks. Test results will be reviewed prior to transitioning from the first day of the screening period to screening period Visit 2, and from screening period Visit 2 to the first day of the treatment period. Re-testing will be performed as necessary.
- [b] During the treatment period, subjects are to visit the study site on the day of dialysis after a 2-day interdialytic interval; however, if this is difficult, subjects are to visit the study site on the day of dialysis after a 1-day interdialytic interval.
- [c] Not required if withdrawn prior to the treatment period.
- [d] Fundoscopy and chest X-ray performed once during screening period, once during Weeks 20–24 of treatment period, and once during Weeks 48–52 of treatment period. In the case of discontinuation of the treatment period, fundoscopy and chest X-ray should be performed within 14 days after discontinuation whenever possible.
- [e] Body weights should be measured before and after dialysis.
- [f] To be measured before dialysis on the day of dialysis during the screening period.
- [g] Tests during the treatment period should be performed before dialysis on the day of dialysis.
- [h] To be performed only in female subjects of childbearing potential.
- [i] Hb levels should be measured in blood collected in the supine position.
- [j] Only Hb levels should be measured.
- [k] Only urea nitrogen levels should be measured before and after dialysis on the first day, Weeks 24 and 52 of the treatment period, and on the day of treatment discontinuation.
- [l] To be measured in the sitting position after a 5-minute rest before blood sampling whenever possible.
- [m] To be measured in the supine position after a 5-minute rest before blood sampling whenever possible.
- [n] AE investigation begins after study drug administration.
- [o] For subjects giving consent to blood sampling for genetic analysis, blood will be collected once as early as possible after Week 2 of the treatment period.

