*2: The first day of the treatment period is the day that notification of subject suitability is received from the online enrollment system.

*3: Fundoscopy and chest X-ray to be performed to extent possible within 14 days of study withdrawal.

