During the screening period, measurements will be made before dialysis whenever the subject makes a study visit on the same day they are scheduled for dialysis. During the treatment period, measurements will be made before dialysis on days the subject is scheduled for dialysis. Measurements will be made before blood sampling when possible, and after 5 minutes at rest.

(7) Fundoscopy

Fundoscopy will be performed once each within the screening period, from treatment period Week 20 to Week 24, treatment period Week 48 to Week 52, and to extent possible within 14 days of study withdrawal. An ophthalmologist will perform the fundoscopy and make evaluations according to the 3-point scale below. Ophthalmologist evaluations will be recorded in CRFs. Fundoscopy images and ophthalmologist evaluations will be stored at study centers and need to be submitted if requested by the study sponsor.

- 1) Normal
- 2) Clinically non-problematic abnormality
- 3) Clinically problematic abnormality (retinal hemorrhage yes/no, retinal oedema yes/no)

(8) Chest X-ray

Fundoscopy will be performed once each within the screening period, from treatment period

Week 20 to Week 24, treatment period Week 48 to Week 52, and to extent possible within 14 days of study withdrawal. Investigators/subinvestigators will evaluate test results according to the 3-point scale below. Evaluation results will be recorded in CRFs. Chest X-rays will be stored at the study center.

- 1) Normal
- 2) Clinically non-problematic abnormality
- 3) Clinically problematic abnormality

(9) Pregnancy tests (only for women who may become pregnant)

Blood sampling and pregnancy testing will be performed on the first day of the screening period, treatment period Weeks 24 and 52, and the day of discontinuation of treatment. Investigators/subinvestigators will evaluate pregnancy based on test results and interview when appropriate. Evaluation results will be recorded in CRFs. If the subject is incapable of becoming pregnant, the reason for this will be recorded in CRFs (women only).

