13.2 Data handling

(1) Definition of missing values

If test measurements are missing or if problems with samples etc. result in invalid measurements or reference values, these are handled as missing values.

(2) Handing of timepoint data for statistical summaries at each measurement timepoint

Statistical summaries for each evaluation timepoint will use data compliant with permitted ranges as described in “Table 9.1-1 Permitted ranges for study center visits.” There will be no supplementing with data from outside the permitted range.

If multiple data points exist within the permitted range, then the one closest to the scheduled day will be used. If there are deviations from the scheduled day, then data points prior to the scheduled day will be used for efficacy evaluation, and data points after the scheduled day will be used for safety evaluation.

(3) Handling of efficacy endpoints if rescue therapy was implemented

No data obtained after implementation of rescue therapy will be used for efficacy evaluation.

(4) Imputation of missing values

Mean Hb values for treatment period Weeks 20 and 24 imputed using LOCF, a method by

which missing timepoints are imputed using data from the immediately prior timepoint (excluding the treatment period start date), will be derived as data for analysis of covariance (ANCOVA) performed as sensitivity analysis for the primary efficacy endpoint. If 1 value is missing, then the closest value to the missing one will be used; if 2 values are missing, then mean Hb will be calculated using 2 different prior values closest to the missing value. Two values from the same timepoint will not be used.

Values imputed by LOCF will also be derived for treatment period Weeks 24 and 52. Data from treatment period Week 24 with missing values imputed will be used as data from the completion of treatment period Phase 1, and data from treatment period Week 52 with missing values imputed will be used as data from the completion of treatment period Phase 2.

(5) Handling of PK-related data

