- [a] The screening period can be up to 6 weeks. Test results should be reviewed prior to transition from the first day of the screening period to screening period Visit 2 and from screening period Visit 2 to the first day of the treatment period. Re-testing can be performed as necessary.
- [b] The scheduled study visit during the treatment period shall be the dialysis day 2 days after the previous dialysis, and if it is difficult, the dialysis day 1 day after the previous dialysis.
- [c] Should not be performed if discontinued before the treatment period.
- [d] Fundoscopy and chest X-ray should be performed once during the screening period. Fundoscopy and chest X-ray should be performed once during Weeks 20–24 of the treatment period, and once during Weeks 48–52 of the treatment period. Should be performed within 14 days after discontinuation whenever possible if discontinued during the treatment period.
- [e] Body weight should be measured before and after dialysis.
- [f] Measurements on the day of dialysis should be performed before dialysis during the screening period.
- [g] Tests during the treatment period should be performed before dialysis on the day of dialysis.
- [h] To be performed only in female subjects of childbearing potential.
- [i] Hb values should be measured in blood collected in the supine position.
- [j] Only Hb values should be measured.
- [k] Only urea nitrogen values will be measured before and after dialysis on the first day, Week 24, and Week 52 of the treatment period and on the day of treatment discontinuation.
- [l] Measurements should be made before blood sampling as much as possible. Measurements should be made in the sitting position after 5 minutes of rest.
- [m] Measurements should be made before blood sampling as much as possible. Measurements should be made in the supine position after 5 minutes of rest.
- [n] AE investigation should begin after study drug administration.
- [o] Blood should be collected once as early as possible after Week 2 of the treatment period for subjects who have given consent to the genetic analysis tests.
- [p] For subjects giving consent to the plasma protein binding rate study, blood should be collected once before study drug administration. Blood collection should be performed before dialysis on the day of dialysis.

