#### **8.6.7 Fundoscopy**

The frequency of each decision result (normal, clinically nonsignificant abnormal, or clinically significant abnormal [Presence or absence of retinal hemorrhage, presence or absence of retinal edema]) should be calculated at each evaluation time point, and a shift table composed of the decision results (normal, clinically nonsignificant abnormal, or clinically significant abnormal) should be provided on the first day of the treatment period and each evaluation time point.

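### Fundoscopy and chest X-ray are scheduled by interval but tabulated by visit window, so a compliant exam on Days 148–160 or 344–356 belongs to no time point in its own table

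*SAP*

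**What the plan says.** **Timing of the exams.** Footnote [d] to the protocol schedule (9.1) reads "Fundoscopy and chest X-ray performed once during screening period, once during Weeks 20–24 of treatment period, and once during Weeks 48–52 of treatment period". The schedule in both SAPs repeats it: "Fundoscopy and chest X-ray should be performed once during Weeks 20–24 of the treatment period, and once during Weeks 48–52 of the treatment period". Protocol 9.2.4.1(7) gives the same timing for fundoscopy, "from treatment period Week 20 to Week 24, treatment period Week 48 to Week 52". The chest X-ray paragraph, 9.2.4.1(8), names fundoscopy by mistake, so the X-ray timing is taken from footnote [d].

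**Which data are tabulated.** Section 7.2 of the Phase 1 SAP and of the final SAP says that data within the Table 9.1-1 ranges "should be used for the tabulation at each evaluation time point and should not be imputed with those outside the permitted range". Protocol 13.2(2) sets the same limit: "There will be no supplementing with data from outside the permitted range". Section 7.2 covers safety as well as efficacy, because its tie-break names both.

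**The windows.** Table 9.1-1 has separate rows for Weeks 20, 24, 48 and 52 and no row for an interval. Its only note on these exams concerns withdrawal: "Fundoscopy and chest X-ray to be performed to extent possible within 14 days of study withdrawal".

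**The tables.** Final SAP 8.6.7 (fundoscopy) and 8.6.8 (chest X-ray) say that the frequency of each result "should be calculated at each evaluation time point, and a shift table composed of the decision results". For fundoscopy the shift table "should be provided on the first day of the treatment period and each evaluation time point". Phase 1 SAP 8.6.6 and 8.6.7 match.

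**The concern.** A site can follow the exam schedule exactly and still produce a result that the tabulation rule cannot place. Protocol 5.4.2 includes fundoscopy to evaluate effects of MT-6548 on the fundus, and only two on-treatment exams are scheduled. An ophthalmologist performs it within an interval rather than on a visit day, so an exam between two visit windows is foreseeable.

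A programmer who applies 7.2 as written drops valid on-schedule results and spreads the rest over two rows, neither of which shows everyone examined. A programmer who keeps those results departs from the plan without a stated rule.

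**Working it through.** **Step 1: reproduce the windows.** Reference day = 7 × week; window = reference day ± 7. All four agree with Table 9.1-1.

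| Visit | Reference day | Window |
|---|---|---|
| Week 20 | 7 × 20 = 140 | 133–147 |
| Week 24 | 7 × 24 = 168 | 161–175 |
| Week 48 | 7 × 48 = 336 | 329–343 |
| Week 52 | 7 × 52 = 364 | 357–371 |

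**Step 2: place each permitted exam day.** With Weeks 20–24 taken as Days 140–168, there are 168 − 140 + 1 = 29 days:

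- Days 140–147 (8 days) fall in Week 20.
- Days 148–160 (13 days) fall in no window.
- Days 161–168 (8 days) fall in Week 24.

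8 + 13 + 8 = 29, and 13/29 = 44.8%. Days 336–364 behave identically: 8 days in Week 48, 13 days (344–356) in none, 8 days in Week 52.

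**Step 3: vary the reading of the interval.**

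- Outer edge to outer edge (Days 133–175 or 329–371): 43 days, of which 15 + 15 are covered and 13 are not; 13/43 = 30.2%.
- Starting one day later (Days 141–168 or 337–364): 13/28 = 46.4%.

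The uncovered days are the same in every case.

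**Step 4: look for a rule that restores these exams.**

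- LOCF in section 7.4 names laboratory values, vital signs and QOL indices, not these exams.
- The SAP errata do not mention them.
- The note to Table 9.1-1 deals only with withdrawal.
- The introduction to section 7 refers to the case review meeting only what section 7 does not already cover. Version 2 of each SAP followed that meeting and contains no exception.

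Baseline is less of a problem. No exam is scheduled on the first treatment day, but 7.4 lets the closest available data stand in for a missing first-day value, which points to the screening exam.

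**Step 5: from days to exams.** The documents do not say on which days exams took place. If they were spread evenly, the share affected would be 30% to 45%: before dropout, 300 × 13/43 ≈ 91 to 300 × 13/29 ≈ 134 exams of each type per interval. If exams cluster at the scheduled visits, it could be near zero. The even-spread figures illustrate scale and do not predict a loss.

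**The case against.** **The windows may not govern these exams.** Table 9.1-1 sets ranges for study visits, and these are interval exams. The range row of the schedule already points to footnote [d] at discontinuation. If the evaluation time point is the interval itself, the table gives no range for it. Handling would then fall to the case review meeting, or to the further rules that protocol 13.2 allows the SAPs to add. Nothing in 7.2 expressly orders an on-schedule exam to be discarded. The SAPs' lists of output tables, not in the text available here, might show how the rows are labelled.

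This shows that a reasonable programmer might keep the exams. It does not remove the problem: 7.2 applies to safety data without exception, the exam tables are by evaluation time point, and no text says which time point an interval exam belongs to.

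**Two stronger readings are not supported.** A reader might infer that abnormal findings vanish from the safety results. Protocol 9.2.4.2(2) makes clinically problematic objective findings adverse events, and 9.2.4.1(7) records retinal hemorrhage and oedema under that grade. Final SAP 8.6.1.1 counts adverse events from dosing to the end of follow-up without visit windows, so those findings are still reported.

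A reader might also infer that 30% to 45% of exams are lost. Those are shares of calendar days only. Nor need the tabulated proportions be biased: if exam timing is unrelated to the result, the counts are too low but the proportions need not be wrong.

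**Conclusion.** The schedule and the tabulation rule conflict. On a literal reading, compliant exams on Days 148–160 and 344–356 are left out of the fundoscopy and chest X-ray frequency and shift tables, and one planned assessment is divided over two rows. The day ranges are exact; the number of exams affected cannot be known from the documents.

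The effect is confined to these two sets of descriptive tables, which carry no test or decision rule. What they can lose is normal results, abnormalities judged non-problematic, the corresponding shifts, and the denominators. The conclusion rests on 7.2 applying to these exams as worded. On the looser reading no exam is lost, but its time point is still undefined. The text should be corrected either way.

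**What to change.** Add to section 7.2 of both SAPs, for fundoscopy and chest X-ray only:

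- The scheduled exam done on Days 133–175 is tabulated as Week 24, and the one done on Days 329–371 as Week 52.
- Discontinuation exams are tabulated separately, so that they do not enter those rows.
- If two exams fall in one interval, the one closest to Day 168 or Day 364 is used. On a tie the later one is used, as 7.2 already provides for safety data.

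Every day of each interval then maps to one row, against 13 unmapped days in each now. Section 10 of each SAP currently reports no departure from the protocol, so this should be recorded there as a change from protocol 13.2(2), with the reason, as protocol 13.4 requires. If the data are already locked, 13.4 also requires the results to be distinguished from the original plan.

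The cost is a short SAP addition and a small change to the visit-mapping program, with no new data or visits and no change to how the exams are done.
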